**IND # 124879**

**Protocol/Study No. DSXS1538a/71515011**

**Desoximetasone 0.25% Shampoo**

---

A frequency summary table of the number of AEs by system organ class, preferred term, severity will be presented. Severity will be classified as “Mild”, “Moderate”, or “Severe”.

Similarly, a frequency summary table of the number of AEs by system organ class, preferred term, and relationship to a study drug will be presented. Relationship to a study drug will be classified as “Not Related” or “Related” where “Related includes “Possible”, “Probable”, or “Definite”.

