**IND # 124879**

**Protocol/Study No. DSXS1538a/71515011**

**Desoximetasone 0.25% Shampoo**

---

Up to 40 patients will be enrolled to obtain 20 evaluable patients with a confirmed diagnosis of moderate to severe scalp psoriasis.

Patients enrolled in the study will apply product once daily for 28 days, according to provided instructions. Each patient is expected to receive 28 doses of study product.

Patients will attend a total of 3 Clinic Visits and a telephone follow-up phone call (Visit 4) as follows:

- **Visit 1 (Day 1):** Screening/Enrollment
- **Visit 2 (Day 14±2):** Interim Visit
- **Visit 3 (Day 29 ± 2):** End of Study or Early Termination
- **Visit 4 (Day 42± 4):** Follow-Up Telephone Phone Call

The primary endpoint is the proportion of patients in the study with HPA axis suppression following treatment with the study medication.

The safety profile of each treatment group will be evaluated by comparing adverse events.

**NOVUM PHARMACEUTICAL RESEARCH SERVICES  
STATISTICAL ANALYSIS PLAN**

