##### **Safety Population:**

Safety Population includes all patients who applied at least one dose of study drug.

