### **6.3.1 Adverse Events**

All the adverse events (AEs) reported throughout the study will be coded and classified according to the MedDRA (Medical Dictionary for Regulatory Activities) coding dictionary. Each adverse event is to be evaluated for date of start and end, seriousness, severity, causal relationship with the study drugs, action taken and outcome.

All AEs will be listed by patient.

A summary table of the number and percent of patients with AEs by system organ class, preferred term will be presented. Each patient will be counted only once within each preferred term.

**NOVUM PHARMACEUTICAL RESEARCH SERVICES  
STATISTICAL ANALYSIS PLAN**

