**T16.1.9.8.1 Summary of Frequency of All Adverse Events by Body System  
(Safety Population)**

| Body System                   | MedDRA Term | Events | Patients   |
|-------------------------------|-------------|--------|------------|
| Patients with at least one AE | Total       | xx     | xx (xx.x%) |
| Ear and labyrinth disorders   | Ear pain    | xx     | xx (xx.x%) |

---

% is based on number of patients included in safety population.

Created on: ddmmmyy hh:mm

Page 1 of N

**T16.1.9.8.2 Summary of Frequency of All Adverse Events in  $\geq 2\%$  of Patients by Body System  
(Safety Population)**

---

**T16.1.9.9 Summary of Frequency of All Adverse Events by Severity  
(Safety Population)**

| Body System                   | MedDRA Term | Mild       | Moderate   | Severe     |
|-------------------------------|-------------|------------|------------|------------|
| Patients with at least one AE | Total       | xx (xx.x%) | xx (xx.x%) | xx (xx.x%) |
| Ear and labyrinth disorders   | Ear pain    | xx (xx.x%) | xx (xx.x%) | xx (xx.x%) |

---

% is based on number of patients included in safety population.

Created on: ddmmmyy hh:mm

Page 1 of N

---

**T16.1.9.10 Summary of Frequency of All Adverse Events by Relationship  
(Safety Population)**

| Body System                   | MedDRA Term | Related    | Not Related |
|-------------------------------|-------------|------------|-------------|
| Patients with at least one AE | Total       | xx (xx.x%) | xx (xx.x%)  |
| Ear and labyrinth disorders   | Ear pain    | xx (xx.x%) | xx (xx.x%)  |

---

Related = Possible, Probable, Definite  
% is based on number of patients included in safety population.

Created on: ddmmmyy hh:mm

Page 1 of N

**T16.1.9.11 Summary of Frequency of Serious Adverse Events  
(Safety Population)**

---

| Body System                                    | MedDRA Term       | Total
N=xx |
|------------------------------------------------|-------------------|---------------|
| Injury, poisoning and procedural complications | Alcohol poisoning | xx            |

---

Created on: ddmmmyy hh:mm

Page 1 of N

**T16.1.9.12 Shift Analysis of Clinical Chemistry Laboratory Results from Baseline to End of Treatment  
(Safety Population)**

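### The adverse event severity and relationship tables count events in the SAP text but base percentages on patients in the shells, and no rule places a patient with several events in one column

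*SAP*

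**What the plan says.** SAP section 6.3.1 describes three adverse event summaries. The first counts patients: "A summary table of the number and percent of patients with AEs by system organ class, preferred term will be presented". It comes with a counting rule: "Each patient will be counted only once within each preferred term". The next two switch to events. For severity: "A frequency summary table of the number of AEs by system organ class, preferred term, severity will be presented". For relationship: "a frequency summary table of the number of AEs by system organ class, preferred term, and relationship to a study drug will be presented". The text mentions no percentage for either of these two, and no rule for a patient with more than one event.

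Shells T16.1.9.9 (severity) and T16.1.9.10 (relationship) label the first row "Patients with at least one AE" and print a single count with a percentage in each column. Their footnotes say that the percentage "is based on number of patients included in safety population". That population is defined in SAP section 5: "Safety Population includes all patients who applied at least one dose of study drug".

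Shell T16.1.9.8.1, the overall table by body system, is laid out differently. It has one column for events and another for patients, and puts the percentage only on patients.

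Protocol section 10.2 says that adverse events will be tabulated, including by severity and relationship, but gives no counting unit and no rule for multiple events.

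**The concern.** A programmer who follows both parts of the SAP takes the numerator from section 6.3.1 (events) and the denominator from the shell (patients). The result is printed in a form that reads as the share of patients affected, but it is not that share once any patient has a repeat event.

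Taking patients as the unit throughout removes the mismatch but leaves a second gap. The count-once rule is attached to the overall table and works only within a preferred term. It does not say whether a patient with a mild and a moderate episode of one term goes in one column or both, nor how to handle a patient with both related and unrelated events. The top row, which pools all terms, has no rule at all.

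The adverse event profile is a named part of the second objective. These are the only tables that show severity and relationship by term. In a study this small, one patient's repeat events visibly move a cell.

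**Working it through.** The documents state no figure on this point, so there is nothing to reproduce. The check sets text against shell and then sizes the difference.

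**Units, side by side**

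| Table | Unit in SAP 6.3.1 | Row label in shell | Percentage base | Rule for several events |
|---|---|---|---|---|
| T16.1.9.8.1, overall | patients | patients, with a separate events column | safety population | once per preferred term |
| T16.1.9.9, severity | events | patients | safety population | none |
| T16.1.9.10, relationship | events | patients | safety population | none |

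**Inputs**

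- Denominator N: SAP section 3 says "Up to 40 patients will be enrolled to obtain 20 evaluable patients with a confirmed diagnosis of moderate to severe scalp psoriasis". I take N = 20 to 40 as the assumed range for the safety population.
- Event rate: the documents give none for this product. The rates and event counts below are assumptions for illustration.

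**Formula under the literal reading**

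Cell % = 100 × (events in cell) / N.

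**Step 1: one patient with repeat events.** One patient has three mild episodes of one term.

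- N = 20: 3/20 = 15%, against a patient share of 1/20 = 5%.
- N = 40: 3/40 = 7.5%, against 1/40 = 2.5%.

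Each extra event moves the cell by 1/40 = 2.5 to 1/20 = 5 percentage points.

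**Step 2: the readings compared.** Assume N = 20 and five patients with events. Four have three mild events each, and one has one mild and one moderate. Mild events = 4 × 3 + 1 = 13; moderate events = 1; total = 14.

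| Reading | Mild | Moderate |
|---|---|---|
| Events over patients (text plus footnote) | 13/20 = 65.0% | 1/20 = 5.0% |
| Events over all events | 13/14 = 92.9% | 1/14 = 7.1% |
| Patients with any event of that grade | 5/20 = 25.0% | 1/20 = 5.0% |
| Patients by worst severity | 4/20 = 20.0% | 1/20 = 5.0% |

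The same data give four different mild cells. Even the two patient-based readings differ: any-grade counting makes 5 + 1 = 6 entries for five patients, while worst-severity counting makes 4 + 1 = 5.

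**Step 3: when a cell passes 100%.** Under the literal reading this needs more events than patients in one cell: at least 21 events at N = 20 (21/20 = 105%) or 41 at N = 40 (41/40 = 102.5%). If the number of events in a cell is Poisson with mean N × m, where m is the mean number of events per patient in that cell, the probability is:

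| m (assumed) | N = 20 | N = 40 |
|---|---|---|
| 0.5 | 0.2% | about 0 |
| 1.0 | 44% | 46% |
| 1.5 | 96% | 99.6% |

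Rates near one event per patient in a single cell are realistic only in the pooled top row, and not there if events are sparse. The overstatement in steps 1 and 2 needs no such rate.

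**The case against.** The best reply is that the shells, read alone, are sound. Their top row names patients and their percentage is over patients, so each cell would be an ordinary incidence that cannot exceed 100%. The mixed ratio appears only when the numerator is taken from section 6.3.1 and the denominator from the shell. That is fair. The documents do not show that the shells use event numerators; they show that text and shell disagree. But if the shells are right, section 6.3.1 is wrong for two tables, and the rule for patients with several events is still missing.

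Second, SAP section 7 presents the shells as a general layout whose headers and footnotes may change after the analysis. That makes the conflict easy to repair but does not resolve it. In an open-label study the counting unit is better fixed before the results are tabulated.

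Third, the information is available elsewhere. T16.1.9.7 and T16.1.9.8.1 report patients with any event, and listing L16.2.7 gives severity and relationship for each event, so a reader could rebuild either table. This stands, and it limits the harm.

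Fourth, counting a patient under both mild and moderate is legitimate if each column means any event of that grade. This also stands. Worst-severity counting is a common convention that the documents do not require; the fault is that the SAP states no convention.

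**Conclusion.** The point holds as a conflict of units plus a missing counting rule. Taken together, the text and the shell footnotes give events per 100 patients shown as a percentage of patients. This overstates the share affected whenever a patient has repeat events: 15% against 5% for one patient with three events at N = 20, and 65% against 20% to 25% in the worked example. These sizes rest on assumed event counts and on N between 20 and 40.

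A reader might infer that the percentages would mean nothing. They would not be meaningless: events over patients is a mean event count per 100 patients, carrying the wrong label. A reader might also infer that the tables will show values above 100%. The documents do not support that. It requires event numerators, which the shells' row label speaks against, and more events than patients in one cell. Nor is a sum across the severity columns evidence of it, because the shell prints no such total.

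The effect is confined to descriptive adverse event tables in a single-arm study. The primary HPA axis analysis does not depend on them.

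**What to change.** Use one unit for numerator and denominator in SAP section 6.3.1 and in shells T16.1.9.9 and T16.1.9.10:

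- Count each patient once per system organ class, once per preferred term and once overall, at maximum severity in T16.1.9.9 and at the strongest relationship in T16.1.9.10. Take the percentage over the safety population.
- If event counts are wanted, give them in a separate column without a patient-based percentage, as T16.1.9.8.1 does.
- State the same rule for the top row that pools all terms.
- In the same edit, state the denominator for the percentages printed below the count of reported events in T16.1.9.7, which has none.

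The cost is a few sentences in the SAP and a shell edit. No data collection changes, because listing L16.2.7 already carries severity and relationship for each event.

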### **6.3.2 Vital Signs**

The patient’s vital signs will be recorded (heart rate, blood pressure, temperature and respiration rate) at Visit 1, 2, and 3.

Vital sign data will be listed by patient and visit.

### **6.3.3 Laboratory Evaluation**

At Visit 1 and Visit 3 a blood sample will be collected for hematology and clinical chemistry testing.

Shift analysis using the categories, below, above and within the laboratory normal range will be performed to identify any specific laboratory parameter that shows a trend toward potentially clinically significant changes.

All data will be listed by patient and visit.

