10.2 Safety Analysis

Safety analysis will be conducted on all patients who applied at least one dose of study product.

Adverse events will be classified using standard MedDRA terminology Version 19 or higher and summarized over all patients. Adverse events reported during the study will be tabulated in summary table listing by type, date of onset, date of resolution, incidence, severity, action taken, outcome and Investigator's opinion of relationship to the study product will be prepared. and symptoms of scalp psoriasis will not be considered adverse events, unless in the Investigator's opinion, they have increased in frequency and/or severity to such an extent that the Investigator/patient considers that it is in the patient's best interest to be dropped from continued participation in the study and given alternative therapy for their condition.

Concomitant medication use during the study will be tabulated by patient.

Ocular safety evaluations will be assessed at the discretion of the Investigator based on the findings of the HEENT exam performed at each visit along with the ocular discomfort reported by the patient. Ocular discomfort will be assessed by patients and reported to staff during clinic visits (Appendix C).

Adverse medical events experienced by the patients will be tabulated. The relationship of AEs, if any, to the study product will be assessed by the Investigator. Adverse events assessed as definite, probable, possible or not related to the study drug will be presented. Shift analysis using the categories, below, above and within the laboratory normal range will be performed to identify any specific laboratory parameter that shows a trend toward potentially clinically significant changes.

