#### **6. STATISTICAL ANALYSIS METHODS**

If not otherwise specified, statistical significance is defined as  $p < 0.05$  and is two-tailed. Data will be summarized with respect to demographic and baseline characteristics, efficacy variables and safety variables.

For categorical variables, the number and percent of each category within a parameter will be calculated for non-missing data. For continuous variables, statistics will include number of observations, mean, standard deviation, median, minimum and maximum values.

All statistical analyses will be conducted using SAS®, Version 9.4 or higher. Datasets will be prepared using headings from Clinical Data Interchange Consortium (CDISC) Study Data Tabulation Model (SDTM) implementation for human clinical trials and ADaM (Analysis Dataset Model).

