**Alanine Aminotransferase (U/L)**

| Baseline->
Endpoint | Low        | Normal     | High       |
|------------------------|------------|------------|------------|
| Low                    | xx (xx.x%) | xx (xx.x%) | xx (xx.x%) |
| Normal                 | xx (xx.x%) | xx (xx.x%) | xx (xx.x%) |
| High                   | xx (xx.x%) | xx (xx.x%) | xx (xx.x%) |

% is based on number of patients included in safety population.

Table will continue for other lab parameters.

Similar table will be created for T16.1.9.13.

**T16.1.9.13 Shift Analysis of Clinical Hematology Laboratory Results from Baseline to End of Treatment  
(Safety Population)**

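### SAP 6.3.3 looks for a laboratory trend but provides no within-patient change, and its shift tables are insensitive to small or moderate change within the normal range

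*SAP*

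**What the plan says.** SAP 6.3.3 has each patient's laboratory values taken twice: "At Visit 1 and Visit 3 a blood sample will be collected for hematology and clinical chemistry testing". It states the purpose of the analysis, to "identify any specific laboratory parameter that shows a trend toward potentially clinically significant changes". The method is carried over from Protocol 10.2: "Shift analysis using the categories, below, above and within the laboratory normal range will be performed". Apart from that, "All data will be listed by patient and visit".

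The SAP Section 7 shells match. T16.1.9.12 shows alanine aminotransferase as a 3×3 low/normal/high table with the note "Table will continue for other lab parameters", and for hematology "Similar table will be created for T16.1.9.13". No shell shows a laboratory mean or a change from baseline. Listings L16.2.8.4 and L16.2.8.5 give individual values with low and high flags.

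Two general statements bear on this. SAP 6 says "For continuous variables, statistics will include number of observations, mean, standard deviation, median, minimum and maximum values", and the sentences leading up to it bring safety variables into the summaries. The introduction to SAP 7 warns that the shells may be incomplete. Neither mentions change from baseline.

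**The concern.** The shift table records a patient as moved only when a reference limit is crossed. A parameter that drifts the same way in most patients but stays inside the range leaves most of them in the normal-to-normal cell. Movement towards a limit, which the stated purpose appears to include, stays invisible until the limit is passed.

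The study has one arm, so the change within each patient is the natural measure of a laboratory effect. Both values are collected, but no planned table puts the difference on the measured scale. What is at stake is how a shift table with few off-diagonal entries can be read: on its own it says little about a modest change in a chemistry or hematology parameter.

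**Working it through.** **Figure to reproduce.** There is none. The documents state no laboratory effect size, SD, power or hypothesis test, and the sample size is given without a calculation (SAP 4). What follows illustrates sensitivity only.

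**From the documents.** Two time points (SAP 6.3.3); 20 evaluable patients (SAP 4) and up to 40 enrolled (SAP 3); two-sided 5% as the general level (SAP 6).

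**Assumed, not in the documents.** Normally distributed values; reference limits at ±1.96 baseline SD; correlation r between visits of 0.5 to 0.8; the same SD at both visits; an upward mean shift stated in baseline SDs.

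**Step 1: paired change, shift 0.5 SD.** SD of change = √(2(1−r)), which is 1.00 at r=0.5 and 0.632 at r=0.8. The standardised effect is 0.5/1.00 = 0.50 or 0.5/0.632 = 0.79. Noncentrality is effect × √n: 2.24 to 3.54 at n=20 and 3.16 to 5.00 at n=40. The paired t-test then has 56% to 92% power at n=20 and 87% to 99.8% at n=40.

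Half-width of the 95% interval for the mean change = t × SD of change / √n:
- n=20: 2.093 × 1.00/4.472 = 0.47 SD; 2.093 × 0.632/4.472 = 0.30 SD.
- n=40: 2.023 × 1.00/6.325 = 0.32 SD; 2.023 × 0.632/6.325 = 0.20 SD.

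**Step 2: shift table, same 0.5 SD shift, patients centred in the range.** The bivariate normal chance of a normal-to-high move is 0.063 (r=0.5) or 0.054 (r=0.8).
- n=20: expected moves 20 × 0.063 = 1.3 or 20 × 0.054 = 1.1. Chance of none: (1−0.063)^20 = 27% or (1−0.054)^20 = 33%.
- n=40: expected moves 2.5 or 2.2. Chance of none about 8% to 11%.

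To put a number on the table, take an exact sign test of all upward against all downward category moves. Five moves in one direction give p = 2 × 0.5^5 = 0.0625 and six give 2 × 0.5^6 = 0.031, so at least six are needed.

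**Step 3: vary the shift and the starting point** (20,000 simulated trials per setting; the 0.5 SD centred row was also checked by exact calculation).

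| Mean shift and start | Sign test, n=20 | Sign test, n=40 | Paired, n=20 | Paired, n=40 |
|---|---|---|---|---|
| 0.5 SD, centred | 0.2–0.4% | about 6% | 56–92% | 87–99.8% |
| 1.0 SD, centred | 10–12% | 60–66% | 99–100% | about 100% |
| 1.5 SD, centred | 64–67% | about 99% | about 100% | about 100% |
| 2.0 SD, centred | about 98% | about 100% | about 100% | about 100% |
| 0.5 SD, starting 1 SD above centre | 10–11% | 35–48% | 56–92% | 87–99.9% |
| 1.0 SD, starting 1 SD above centre | 63–73% | 96–99.5% | 99–100% | about 100% |

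**Step 4: price of the added intervals.** Appendix F names 7 chemistry and 6 hematology items, 13 in all, with the differential count as one item. With no true change, 13 × 0.05 = 0.65 intervals are expected to exclude zero, and somewhat more once the differential is split.

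**The case against.** **SAP 6 already covers safety variables, and the shells are only a framework.** This stands in part: laboratory means by visit may already be promised. It would therefore be wrong to infer that the SAP as a whole allows nothing but categories. But where the SAP intends by-visit statistics it says so and supplies a shell, as for percent scalp affected (6.1.4, T16.1.9.5). Visit-wise means and SDs also do not give the SD of the change or its interval, so the pairing is lost.

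**The stated purpose need not mean a mean change.** The documents speak of a trend and never of a group trend. Crossing a reference limit is a reasonable way to look for changes nearing clinical significance. This too stands in part: the wording is loose rather than contradicted. It does not help with movement towards a limit that has not yet been crossed.

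**The power contrast tests nothing in the plan.** Correct. No laboratory test is specified, and the proposed addition is descriptive. The figures show how much information the categories discard; they do not correct a stated calculation.

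**The shift table is not blind.** Also correct. A reader might infer that it cannot show any shared change, or would be essentially empty. The larger shifts in Step 3 contradict the first. The second fails because, even at 0.5 SD and n=20, about two thirds to three quarters of trials would show at least one normal-to-high move.

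**Vital signs.** A reader might extend the point to SAP 6.3.2, where "Vital sign data will be listed by patient and visit". That section states no trend purpose, so the mismatch does not arise there.

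**Conclusion.** The point holds in a limited form. SAP 6.3.3 sets out to find a laboratory trend, and neither it, its shells nor the general rule in SAP 6 provides the within-patient change. At 20 to 40 patients the shift table is very insensitive to change of about 0.5 SD inside the range: under 0.5% and about 6% on the illustrative sign test, against 56–92% and 87–99.8% for the paired change. It is adequate for shifts of about 1.5 SD or more, and at n=20 has 63–73% for about 1 SD when patients start near a limit. These figures rest on assumed normality, limits at ±1.96 SD and correlation 0.5 to 0.8.

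A reader might infer that the report will declare the absence of a trend. No document says so, and every value is listed with range flags. A reader might also infer that nothing outside the SAP called for three categories. Protocol 7.3 and 9.2 rest the design partly on regulatory advice that is not reproduced, so this cannot be settled here. The laboratory data are ancillary to the HPA endpoint, and no primary conclusion changes. This is a minor improvement.

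**What to change.** In SAP 6.3.3:

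- Keep T16.1.9.12 and T16.1.9.13 for threshold crossings.
- For each laboratory parameter, add Visit 1, Visit 3 and paired change (n, mean, SD, median, minimum, maximum) with a 95% confidence interval for the mean change. Use patients with both values, and state that denominator, because the shift shells use the whole safety population.
- Label the table descriptive, since SAP 6.4 makes no multiplicity adjustment.
- State that trend is read from the paired change and threshold crossings from the shift table.
- Add the shells to SAP 7.

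The cost is a wording change and one or two standard tables from data already collected, with no new patients or procedures. The drawback is that about 1 in 20 intervals will exclude zero by chance, so single exclusions should not be read as findings. A matching vital-signs table is optional.
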